3.9 Study Population

For entry into the study, the following criteria MUST be met prior to dosing on Day 1. No exceptions will be granted.

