 - 3) Prior therapy requirement: Subjects must have received and then progressed or have been intolerant or refractory to at least 1 standard systemic therapy (eg, platinum-based chemotherapy) for metastatic and/or unresectable disease. Subjects who are sensitive to platinum must have received at least 2 prior platinum-containing lines of treatment.
- vi. Hepatocellular Carcinoma - Cohort 8**
- 1) Subjects must have progressive disease, or been intolerant to, at least one line of therapy or refuse treatment with sorafenib.
 - 2) Child-Pugh score of 6 points or less and must not have encephalopathy and total bilirubin $\leq 1.5 \times$ upper limit of normal (ULN; ie, Child Pugh A)
 - 3) Subjects must have testing for hepatitis B surface antigen (HBsAg), hepatitis B surface antibody, hepatitis B core antibody, hepatitis B DNA polymerase chain reaction (PCR), hepatitis C antibody, or hepatitis C RNA PCR.
 - 4) Subjects with hepatitis B infection must have hepatitis B DNA viral load < 100 IU/mL and must be on anti-viral therapy per institutional guidelines.
 - 5) Subjects with hepatitis B infection must not have co-infection with hepatitis C or hepatitis D (must obtain hepatitis D antibody testing).
 - 6) Subjects must not have clinically significant ascites or clinically significant variceal bleeding.
- vii. Solid tumors types as listed in part D are a part of Cohort 10, Part E**
- 1) Subjects with NSCLC (prior I/O therapy), bladder, SCCHN, ovarian cancer and hepatocellular cancer. Must meet inclusion criteria listed in part D. Must not meet exclusion criteria
 - 2) Must have received, and then progressed or been intolerant to, at least one standard treatment regimen in the advanced or metastatic setting, if such a therapy exists must meet inclusion criteria as stated above. Subjects who refuse or are

ineligible for standard therapy will be allowed to enroll provided their refusal/ineligibility is documented in medical records

h) Conditions for all tumor types

- 
- 2) Not applicable for revised protocol 03
 - 3) Subjects must have ≤ 5 prior treatment regimens. The following are not considered separate lines of treatment: addition of a compound to an on-going regimen, re-starting the same regimen after a drug holiday, or switching from IV to oral therapy.

Parts A-E:

Not applicable as of revised protocol 03.

Adequate organ function for subjects with solid tumor histologies, which is defined as follows:

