- 1) White blood cell $\geq 2000/\mu\text{L}$ (stable off any growth factor within 4 weeks of first study drug administration)
- 2) Neutrophils $\geq 1500/\mu\text{L}$ (stable off any growth factor within 4 weeks of first study drug administration)
- 3) Platelets $\geq 100 \times 10^3/\mu\text{L}$ (transfusion to achieve this level is not permitted within 2 weeks of first study drug administration) subjects with hepatocellular cancer $\geq 60 \times 10^3/\mu\text{L}$
- 4) Hemoglobin $\geq 8.5 \text{ g/dL}$ (transfusion to achieve this level is not permitted within 2 weeks of first study drug administration)
- 5) Alanine aminotransferase (ALT) and aspartate aminotransferase (AST) $\leq 3x \text{ ULN}$ subjects with hepatocellular cancer $\leq 5x \text{ ULN}$

- 6) Total bilirubin $\leq 1.5 \times$ ULN (except subjects with Gilbert's Syndrome who must have normal direct bilirubin) subjects with hepatocellular cancer Bilirubin < 3 mg/dL
- 7) Normal thyroid function or stable on hormone supplementation per Investigator assessment
- 8) Serum creatinine $\leq 1.5 \times$ ULN or creatinine clearance (CrCl) ≥ 40 ml/min (measured using the Cockcroft-Gault formula below):
Female CrCl =
$$\frac{(140 - \text{age in years}) \times \text{weight in kg} \times 0.85}{72 \times \text{serum creatinine in mg/dL}}$$

Male CrCl =
$$\frac{(140 - \text{age in years}) \times \text{weight in kg} \times 1.00}{72 \times \text{serum creatinine in mg/dL}}$$
- 9) Albumin > 2.8 mg/dL
- 10) Ability to comply with treatment, PK [REDACTED] sample collection, and required study follow-up.
- 11) Subject Re-enrollment: This study permits the re-enrollment of a subject that has discontinued the study as a pre-treatment failure (e.g., subject has not been treated). If re-enrolled, the subject must be re-consented.

3) Age and Reproductive Status

- a) Men and women, ages ≥ 18 years at the time of informed consent
- b) Women of childbearing potential (WOCBP) must have a negative serum or urine pregnancy test (urine pregnancy test: minimum sensitivity 25 IU/L or equivalent units of human chorionic gonadotropin [hCG]) within 24 hours prior to the start of study drug.
- c) Women must not be breastfeeding.
- d) WOCBP must agree to follow instructions for method(s) of contraception for the duration of treatment with study drug (s) plus 5 half-lives of study drug plus 30 days (duration of ovulatory cycle) for a total of 23 weeks post-treatment completion.

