Eligibility criteria for this study have been carefully considered to ensure the safety of the study subjects and that the results of the study can be used. It is imperative that subjects fully meet all eligibility criteria.

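### The albumin item of the organ-function criteria is printed in mg/dL, 1000-fold below the g/dL scale of the protocol's own Appendix 5, and as printed cannot realistically be failed

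*Combined protocol and SAP*

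**What the plan says.** Section 3.9.1 of the protocol introduces the organ-function list with "Adequate organ function for subjects with solid tumor histologies, which is defined as follows", under a heading that covers Parts A to E. Item 9 of that list is "Albumin > 2.8 mg/dL".

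The criteria are binding. Section 3.9 requires them to be met before dosing on Day 1 and adds "No exceptions will be granted". Section 3.9.2 closes with "It is imperative that subjects fully meet all eligibility criteria".

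Appendix 5 tabulates albumin in g/dL for the Child-Pugh score: above 3.5 scores 1 point, 2.8 to 3.5 scores 2, and below 2.8 scores 3. The hepatocellular criteria (Cohort 8, extended to Cohort 10 because its subjects must meet the Part D criteria) require "Child-Pugh score of 6 points or less and must not have encephalopathy".

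Tables 5.1-1, 5.1-2 and 5.1-3 and Section 5.3.2 name albumin as a laboratory test but give no unit.

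**The concern.** One number, 2.8, appears for one analyte in two units that are 1000-fold apart, and one of the two places is an operative entry threshold. A threshold that no screened subject could fail does no work, whatever its authors intended.

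At stake is whether the protocol text defines who was eligible. Take a subject with albumin of 2.5 g/dL. That subject complies with item 9 as printed and fails it if the same number is read in g/dL. Whether enrolling that subject is a protocol deviation then depends on who reads the item. Under criteria that allow no exceptions, that should be settled by the text.

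**Working it through.** **Inputs.**
- Printed limit: above 2.8 mg/dL (Section 3.9.1, adequate organ function, item 9).
- Albumin scale: g/dL, with band edges at 2.8 and 3.5 (Appendix 5).
- Hepatocellular limit: Child-Pugh total no higher than 6 (Section 3.9.1).
- Conversion: 1 g = 1000 mg.

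The plan derives no figure here, so there is nothing to reproduce. The check is a unit conversion and a comparison of the two places.

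**Step 1. Convert the printed limit.** 2.8 mg/dL ÷ 1000 = 0.0028 g/dL. In the other direction, 2.8 g/dL × 1000 = 2800 mg/dL. The ratio is 2800 ÷ 2.8 = 1000.

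**Step 2. Apply both readings to example values.**

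| Albumin (g/dL) | In mg/dL | Passes as printed (> 2.8 mg/dL) | Passes if 2.8 is read in g/dL |
|---|---|---|---|
| 0.0028 | 2.8 | no | no |
| 0.01 | 10 | yes | no |
| 1.0 | 1000 | yes | no |
| 2.5 | 2500 | yes | no |
| 2.8 | 2800 | yes | no |
| 3.0 | 3000 | yes | yes |

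The value 0.01 g/dL is 2.8 ÷ 0.01 = 280 times below the lowest band edge in Appendix 5, and it still passes as printed. Of the range from 0 to 2.8 g/dL, only 0.0028 ÷ 2.8 = 0.1% fails.

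**Step 3. Is albumin limited elsewhere?** For hepatocellular expansion subjects, yes. Appendix 5 scores five measures from 1 to 3 points each. Albumin below 2.8 g/dL scores 3. With the other four at their minimum of 1, the total is 4 + 3 = 7, which exceeds 6. These subjects are excluded whatever item 9 says. No other albumin limit was found in the available text for the NSCLC, cervical, bladder, head and neck or ovarian cohorts, or in the tumor-agnostic dose escalation.

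**Step 4. Is the unit likely to be an extraction error?** The same list gives hemoglobin in g/dL, and the hepatocellular bilirubin limit and the creatinine in the clearance formula in mg/dL. Both units therefore came through in neighbouring items. A misread cannot be ruled out from the text alone, but nothing points to one.

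**The case against.** The strongest reply is that this is a copy-edit. Because 2.8 is an albumin band edge in g/dL in the protocol's own appendix, sites can easily infer what was meant. Albumin is measured by local laboratories with their own reference ranges, and Section 5.3.2 asks for correct units when they differ from the case report form. Other safeguards remain: transaminase and bilirubin limits, the hepatitis exclusions, and exclusion 2(s), which covers any condition judged hazardous. Most of this stands, and it is why the point is minor. It does not remove the mismatch: if sites read the item in g/dL, practice and protocol text differ.

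Four stronger readings are tempting, and the documents do not support them.

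- **That the whole organ-function criterion excludes nobody.** Only the albumin item is affected. The limits on white cells, neutrophils, platelets, hemoglobin, transaminases, bilirubin, thyroid function and renal function still exclude subjects.
- **That 2.8 marks the worst Child-Pugh class.** It bounds the 3-point albumin band. The worst class, C, is set by a total of 10 to 15 points.
- **That edit checks were coded in mg/dL, or that deviations went unflagged.** The documents do not describe how the item was coded or applied. This is something to confirm, not something shown.
- **That Appendix 5 settles the right limit.** It is a scoring table and sets no albumin entry limit for other tumors. Even in g/dL, item 9 would reject a value of exactly 2.8, which the appendix places in its middle band, so the two do not match exactly at the boundary.

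**Conclusion.** The point holds for the albumin item. Section 3.9.1 and Appendix 5 differ by a factor of exactly 1000, and as printed the item cannot realistically be failed. The documents give no albumin distribution, so this assumes that no screened subject has a value at or below 0.0028 g/dL, an assumption with a very wide margin given Step 2. A unit slip is the likely cause, because the number coincides with an appendix band edge, but that is an inference.

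The practical reach is limited. Hepatocellular expansion subjects are covered by another route, and nothing shows that any subject was enrolled on the literal reading. What remains is a binding eligibility item whose text does not define eligibility for the other tumor types. No endpoint, sample size, power or error rate depends on it. It is a low-severity inconsistency.

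**What to change.** The sponsor should reconcile item 9 of the organ-function list with Appendix 5 and state the intended albumin limit and its unit, including whether the boundary value itself qualifies. Which limit applies is a clinical decision for the sponsor; this review does not propose one.

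The sponsor should also confirm which unit was applied in eligibility review and in deviation review. If enrollment is already largely complete at this revision, which the documents do not state, that confirmation is the more useful half. A listing of baseline albumin with units, checked against the stated limit, would show whether any subject's status changes.

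The cost is one corrected line in the protocol, one check of the eligibility and deviation specifications, and one short listing of data already required by the screening schedule. No analysis needs to change.

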Part E will consist of an initial safety lead in period of up to 12 subjects. Six subjects need to complete the 14-day observation period before the full expansion cohorts, of up to 40 subjects, are opened. Patients who discontinue for reasons other than disease progression, death, or treatment-related toxicity may be replaced. An observation period of 14 days has been chosen based on pharmacokinetic (PK) modeling and simulation for BMS-986156, based on PK parameters derived from preclinical studies (Section 1.1.5).

Duration of Study: The total duration of time for any individual subject in both monotherapy and combination arms of the study is expected to be approximately 3.1 years.

Number of Subjects: Approximately 310 subjects will be dosed.

Study Population:

Male and/or female subjects who are at least 18 years old, and satisfy eligibility criteria by medical history, physical examination (PE), 12-lead electrocardiogram (ECG), and clinical laboratory evaluations will be included to participate in the study as follows:

For Dose Escalation in Parts A and B: Subjects with any solid tumor type (with the exception of primary central nervous system tumors) are eligible to enroll. All subjects will be required to document availability of archival tumor tissue before study drug is administered. If archival tumor tissue is not available, subjects must consent to a tumor biopsy.

For Cohort Expansion (Parts C, D, and E): Subjects must have one of the tumor types defined above.

Women of childbearing potential (WOCBP) must not be nursing or pregnant and must be using an acceptable method of contraception for at least 4 weeks before dosing. WOCBP must have a negative pregnancy test within 24 hours prior to dosing with study medication.

Study Drug: Includes Investigational Product (IP) as listed:

Study Drug for BMS-986156 and Nivolumab

Medication	Potency	IP/Non-IP
BMS-986156 Injection	100 mg/vial (10 mg/mL)	IP
nivolumab Injection	100 mg/vial (10 mg/mL)	IP

Study Assessments:

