- e) Males who are sexually active with WOCBP must agree to follow instructions for method(s) of contraception for the duration of treatment with study drug (s) plus 5 half-lives of study drug (s) plus 90 days (duration of sperm turnover) for a total of 31 weeks post treatment completion.
- f) Azoospermic males and WOCBP who are continuously not heterosexually active are exempt from contraceptive requirements. However WOCBP must still undergo pregnancy testing as described in this section.

Investigators shall counsel WOCBP and male subjects who are sexually active with WOCBP on the importance of pregnancy prevention and the implications of an unexpected pregnancy. Investigators shall advise WOCBP and male subjects who are sexually active with WOCBP on the use of highly effective methods of contraception. Highly effective methods of contraception have a failure rate of $< 1\%$ when used consistently and correctly.

At a minimum, subjects must agree to the use of two methods of contraception, with one method being highly effective and the other method being either highly effective or less effective as listed below:

HIGHLY EFFECTIVE METHODS OF CONTRACEPTION

Highly effective methods of contraception have a failure rate of $< 1\%$ when used consistently and correctly. WOCBP and female partners of male subjects who are WOCBP are expected to use one of the highly effective methods of contraception (listed below). Local laws and regulations may require use of alternative and/or additional contraception methods. Male subjects must inform their female partners who are WOCBP of the contraceptive requirements of the protocol and are expected to adhere to using contraception with their partner. Male subjects are expected to use a condom, in addition to a highly effective method as noted in the list below

- 1) Progestogen only hormonal contraception associated with inhibition of ovulation
- 2) Hormonal methods of contraception including oral contraceptive pills containing combined estrogen and progesterone, vaginal ring, injectables, implants, and intrauterine devices (IUDs), such as Mirena®
- 4) Nonhormonal IUDs, such as ParaGard®
- 5) Bilateral tubal occlusion
- 6) Vasectomized partner with documented azoospermia 90 days after procedure
 - Vasectomy is a highly effective birth control method provided that the partner is the sole sexual partner of the WOCBP study participant and that the vasectomized partner has received medical assessment of the surgical success.

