- 7) Intrauterine hormone-releasing system
- 8) Complete abstinence
 - Complete abstinence is defined as the complete avoidance of heterosexual intercourse (refer to Glossary of Terms, [Section 10](#))
 - Complete abstinence is an acceptable form of contraception for all study drugs and must be used throughout the duration of the study treatment (plus 5 half-lives of the study drug(s) plus 30 days).
 - It is not necessary to use any other method of contraception when complete abstinence is elected.
 - Subjects who choose complete abstinence must continue to have pregnancy tests, as specified in [Section 5.1](#).
 - Acceptable alternate methods of highly effective contraception must be discussed in the event that the subject chooses to forego complete abstinence.
 - The reliability of sexual abstinence needs to be evaluated in relation to the duration of the clinical study and the preferred and usual lifestyle of the subject.
- 9) Use a condom in male subjects with female partners.

UNACCEPTABLE METHODS OF CONTRACEPTION

- 1) Periodic abstinence (calendar, symptothermal, and/or post-ovulation methods)
- 2) Withdrawal (coitus interruptus)

- 3) Spermicide only
- 4) Lactation amenorrhea method
- 5) Diaphragm with spermicide
- 6) Cervical cap with spermicide
- 7) Vaginal sponge with spermicide
- 8) Male or female condom with or without spermicide*
- 9) Progestogen-only oral hormonal contraception, where inhibition of ovulation is not the primary mode of action.

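### Section 3.9.1 cannot be applied as written: it points to a list of less effective contraceptive methods that is not there, and it gives condoms two opposite statuses

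*Combined protocol and SAP*

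**What the plan says.** Section 3.9.1, under Age and Reproductive Status, sets the rule in several places.

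- The general rule: "At a minimum, subjects must agree to the use of two methods of contraception, with one method being highly effective", with "the other method being either highly effective or less effective as listed below".
- The next paragraph, under the highly effective heading: "WOCBP and female partners of male subjects who are WOCBP are expected to use one of the highly effective methods of contraception (listed below". It defines these methods by a failure rate below 1% and expects male subjects to add a condom to a highly effective method.
- Item 9 of the highly effective list: "Use a condom in male subjects with female partners".
- Item 8 of the unacceptable list: "Male or female condom with or without spermicide". Items 5 to 7 of that list are the diaphragm, cervical cap and vaginal sponge, each with spermicide.
- Exemptions: azoospermic men, women who are continuously not heterosexually active, and subjects who choose complete abstinence, who need no other method.

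The Study Population part of the synopsis says that WOCBP "must be using an acceptable method of contraception for at least 4 weeks before dosing". The glossary (Section 10) releases abstinent subjects from a second method. Section 3.9 makes all entry criteria mandatory without exception.

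**The concern.** A criterion that admits no exceptions has to give one answer for one person. Here the text refers the site to a list that it does not contain, and it classes the same method as both highly effective and unacceptable. Two sites could decide differently on the same subject, and a monitor would have no fixed standard for calling a deviation.

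The rule also continues after enrolment. It binds subjects through treatment, which Section 3.2 allows to run to 13 cycles (13 × 8 = 104 weeks), and then for 23 weeks in women and 31 weeks in men. Section 1.6 gives the reason for caution: late pregnancy loss and early infant death in monkeys exposed to nivolumab.

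**Working it through.** No power, rate or sample-size figure is involved, so the check sets the passages side by side and tries them on cases.

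**1. The missing list.** The general rule points forward to a list that should name less effective methods. Two lists follow. One is headed highly effective and the other unacceptable. The diaphragm, cap, sponge and condom are all in the second. No permitted less effective method is named anywhere. Read literally, the second method must then be another highly effective one, which leaves the less effective option with no content.

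**2. Condoms.** They have three statuses in Section 3.9.1: a member of the highly effective list (item 9), a member of the unacceptable list (item 8), and an addition to a highly effective method for men. The third implies that a condom is something other than a highly effective method, which contradicts the first. The second contradicts both.

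**3. Number of methods.** The general rule says two. The following paragraph says one of the highly effective methods. The synopsis uses the singular. The glossary presupposes a second method for anyone who is not abstinent.

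**4. Pre-dose period.** The synopsis asks for at least 4 weeks. Section 3.9.1 covers treatment and the weeks after it and sets no period before dosing.

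**Cases.**

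- *Woman with a non-hormonal IUD only:* meets the one-method sentence; fails the two-method sentence.
- *Woman with an IUD plus a diaphragm with spermicide:* has two methods, one highly effective; the second is of the kind a less effective list might hold but is classed as unacceptable.
- *Woman with an IUD plus her partner's condom:* the condom is on the unacceptable list; item 9 would count it, but item 9 is worded for male subjects, so whether it covers her partner is itself unclear.
- *Man using a condom whose partner has an IUD:* does what the male instruction asks, with a method that appears in both lists.
- *Woman who started a highly effective method less than 4 weeks before dosing:* fails the synopsis on timing; nothing on timing in Section 3.9.1 excludes her.
- *Subject choosing complete abstinence:* one method, expressly allowed; no conflict.

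**What still protects.** Table 5.1-2 schedules a pregnancy test at each dosing visit, within 24 hours before study drug, and holds drug if it is positive. Table 5.1-3 repeats testing at Days 30, 60 and 100. Women's post-treatment contraception lasts 23 × 7 = 161 days. If both periods are counted from the last dose, 161 − 100 = 61 days have no scheduled test. The male period is 31 × 7 = 217 days, and no test is scheduled for partners. Testing reduces the consequence of the ambiguity but does not cover the whole period.

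**The case against.** The strongest reply is that two methods against one is not a proven contradiction. The one-method sentence sits under the highly effective heading and can be read as describing the highly effective half of a pair. The glossary supports this, and for men a condom plus a highly effective method also makes two. This stands. A reader might infer that the protocol flatly demands both one and two methods; the text does not establish that. It does fail to say which is meant, and the singular in the synopsis adds to the doubt.

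Text may also have been lost. Item 8 carries an asterisk without a footnote, and the highly effective list skips item 3. A footnote might qualify the condom entry among the unacceptable methods. It would not supply the missing list or explain a condom among methods defined by failure below 1%. A lost item 3 would belong to the highly effective list and could not be a separate one.

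The 4-week requirement is silence in Section 3.9.1, not conflict, since a site can satisfy both texts. That is correct, and the two places should simply agree.

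A reader might infer that a couple relying on condoms alone could be accepted through item 9. That would mean disregarding the two-method minimum, the instruction that men add a condom to another method, and the unacceptable list. Item 9 reads more like the male instruction placed in the wrong list.

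**Conclusion.** The point holds on two firm grounds, the absent list and the contradictory status of condoms. Two lesser ones stand beside them: an unclear number of methods, and a pre-dose period found only in the synopsis. It matters because the criterion is binding and protects subjects and pregnancies. It changes no endpoint, estimate, sample size or decision rule.

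The conclusion assumes that the supplied text of Section 3.9.1 is complete apart from a possible footnote at the asterisk and a possible item 3. The consent pages were not available, so what subjects are told cannot be judged.

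The people concerned are non-exempt WOCBP and non-exempt men with WOCBP partners. How many there are cannot be derived. A reader might take the planned enrolment of the cervical and ovarian cohorts as the size: Cohorts 2, 4, 7 and 9 give 25 + 40 + 40 + 40 = 145. That counts all subjects, whereas Section 3.9.3 excludes postmenopausal women and those with a hysterectomy or bilateral oophorectomy, and no WOCBP fraction is given. It also leaves out ovarian subjects in Cohort 10, and becomes 160 if Cohort 2 has the 40 subjects stated at one place in Section 3.1. Neither figure should be used.

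Nor do the documents support saying that the pregnancy safeguard has failed. Apart from abstinence, and unless item 9 is taken literally, the readings of Section 3.9.1 share a floor of one highly effective method, and testing continues. The safeguard is ambiguous, not void.

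**What to change.** Reconcile the synopsis (Study Population), Section 3.9.1 and the glossary, and check the consent wording against the result:

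- state one required number of methods, and say whether the one-method sentence describes part of a pair;
- make the reference to less effective methods match an actual list, or remove it;
- give condoms a single status, and move the instruction to male subjects out of the highly effective list;
- resolve the asterisk on the condom item in the unacceptable list;
- make the synopsis and Section 3.9.1 agree on any period before dosing.

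The sponsor decides which clinical rule applies; the request is only that the passages say the same thing. The cost is a wording amendment, which needs IRB/IEC approval under Section 9.1.1, and a matching consent update where the consent text is affected. No analysis changes.
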